## 6.0 Health Related Quality of Life (HRQL)

To assess HRQL, subjects will be assessed using the Functional Assessment of Cancer Therapy—Hepatobiliary (FACT-Hep) Questionnaire (Appendix D). This 45-item self-report instrument is designed to measure HRQL in patients with hepatobiliary cancers and is one of the most widely-used instruments in this clinical area. The FACT-Hep consists of the 27-item FACT-G, which assesses generic HRQL, and the 18-item Hepatobiliary Subscale (HS), which assesses disease-specific issues such as pain, appetite, and cramping. The FACT-G is divided into four HRQL domains: physical well-being (7 items), social/family well-being (7 items), emotional well-being (6 items), and functional well-being (7 items). All items have a 7-day reference period and are scored from 0-4 (“not at all” to “very much”), with higher scores indicating better HRQL. Score ranges are 0-28 for physical well-being, 0-28 for social/family well-being, 0-24 for emotional well-being, 0-28 for functional well-being, and 0-72 for HS. All subscale scores from the FACT-G and HS can be summed together to create a total FACT-Hep score, with a possible range of 0-180. The FACT-Hep takes approximately 10 minutes to complete.

Subjects assigned to the SBRT arm will complete the FACT-Hep at baseline/screening, at the time of the second fraction of the SBRT treatment (post treatment prior to discharge), on the last day of treatment (post treatment prior to discharge), 2 weeks after treatment, and at the time of follow-up scans at 3, 6, 9, 12, 15, 18, 21 and 24 months from randomization or until liver transplantation.

Subjects assigned to the TACE arm will complete the FACT-Hep at baseline/screening, TACE treatment #1(post treatment prior to discharge), 2 weeks after treatment #1, at TACE treatment #2 (post treatment prior to discharge), 2 weeks after treatment #2, at TACE treatment #3(post treatment prior to discharge), and 2 weeks after treatment #3. The number of TACE treatments will vary from 1 to 3, so not all HRQL assessments will be collected for all subjects. The HRQL assessment at the time of the last TACE will serve as the HRQL assessment on the last day of treatment, while the HRQL assessment done 2 weeks after the last TACE assessment will serve as the 2 weeks after treatment assessment. HRQL will then continue to be collected at the time of follow up scans at 3, 6, 9, 12, 15, 18, 21 and 24 months from randomization or until transplantation.

## 7.0 Study Calendars

**Table 2: Study Calendar for SBRT (Arm A)**

Active Treatment-SBRT	Pre-Rx Eval  (screening)	SBRT fractions (5 in 2 week period) 	Last fraction of treatment (prior to discharge)	2 Week Follow up post treatment (+/- 3 days)
History and Physical Exam	X			X
Weight	X			X
CBC with differential	X 			X
AST, ALT, Alk Phos, Total Bilirubin, Albumin	X 			X
Na, BUN/Creatinine	X 			X
INR	X 			X

AFP (for HCC)	X 			
Toxicity Notation	X		X	X
Multiphasic MRI or CT of the abdomen within 4-6 weeks prior to enrollment	X			
Chest CT or Chest x-ray within 1 year prior to enrollment	X			
MELD-Na, ALBI, and CTP assessment	X 			X
HRQL 	X	X 	X	X
Randomization 	X			
Simulation	X			
Treatment: SBRT 		X (over a two week period)		

 Within 2 weeks prior to randomization unless otherwise specified

 If multiple lab results are available within the screening period, use the most recent results before randomization.

 If calculations are performed multiple times, use the most recent value before randomization

 HRQL questionnaire: FACT-Hep

 Randomization may occur after all screening procedures are complete and eligibility has been met. See section 3.0 for more details.

Initial treatment should be scheduled within 3 weeks of randomization.

See section 6.0 for details on HRQL administration timelines.

**Table 3: Study Calendar for TACE (Arm B)**

Active Treatment – TACE					
	Pre-Rx Eval  (screening)	Initial TACE	2 week Follow up post initial TACE (+/- 3 days)	Second and Following TACE treatments	2 week Follow up post TACE (+/-3 days)
History and Physical Exam	X	X	X (per MD SOC only)	X	X (per MD SOC only)
Weight	X	X	X	X	X
CBC with differential	X 	X 	X	X 	X
AST, ALT, Alk Phos, Bilirubin, Albumin	X 	X 	X	X 	X
Na, BUN/Creatinine	X 	X 	X	X 	X
INR	X 	X 	X	X 	X
AFP (for HCC)	X 	X 		X 	
Toxicity Notation	X	X	X	X	X
MRI or CT of the abdomen within 4-6 weeks prior to enrollment	X				

Chest CT or chest x-ray within 1 year prior to enrollment	X				
MELD-Na ALBI, and CTP assessment	X 		X		X
HRQL 	X	X 	X	X 	X
Randomization 	X				
Treatment:TACE 		X		X	

 Within 2 weeks prior to randomization unless otherwise specified.

 If multiple lab results are available within the screening period, use the most recent results before randomization.

 If calculations are performed multiple times, use the most recent value before randomization.

 HRQL questionnaire: FACT-Hep

 See section 6.0 for details on HRQL administration timelines.

 Randomization may occur after all screening procedures are complete and eligibility has been met. Initial treatment should begin within 3 weeks of randomization. See section 3.0 for details on randomization.

 If required labs were performed within 3 days of a TACE procedure, they do not have to be repeated unless requested by treating physician.

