#### 17.2.3 Other Secondary Endpoints

Quantitative outcomes like number of retreatments and number of toxicities will be described by mean, standard deviations, median, minimum and maximum by treatment group and treatment group will be compared using a t-test. Categorical outcomes like any retreatment, any toxicity, radiologic response, pathologic response will be described by counts, percent and groups compared using the chi-square test. Overall survival, and 60 day post-transplant morbidity and mortality will be described by Kaplan-Meier estimates, and groups compared using the log-rank test and Cox model as for the primary outcome. Note, with 98 patients per arm, each arm will have 99% and 95% probabilities of observing at least one event of toxicity when the true probabilities per patient are 0.05 and 0.03. Further, when estimating proportion of patients to have a particular toxicity, the 95% confidence intervals will have precision of 10% or tighter, for each treatment group.

We will analyze secondary endpoints relating to time to event analogously to time to recurrence, and quantitative outcomes analogously to the analysis the HRQL endpoints.

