## F. APPENDICES

### Appendix A: Model for End-Stage Liver Disease (MELD-Na) and Child-Turcotte-Pugh (CTP)

The MELD-Na score includes serum sodium level. Sodium has been added to the formulation (*as of January 2016*) and is calculated using a relatively simple formula that relies on four readily available objective variables:

- Serum creatinine (Scr; mg/dL)
- Total bilirubin (Tbil; mg/dL)
- INR (international normalized ratio)
- Serum sodium (mmol/L)

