#### Child-Turcotte-Pugh (CTP)

	Points		
	1	2	3
Encephalopathy	None	Grade 1-2 (or precipitant-induced)	Grade 3-4 (or chronic)
Ascites	None	Mild/Moderate (diuretic-responsive)	Severe (diuretic-refractory)
Bilirubin (mg/dL)	<2	2-3	>3
Albumin (g/dL)	>3.5	2.8-3.5	<2.8
PT (sec prolonged) or INR	<4 <1.7	4-6 1.7-2.3	> 6 >2.3

CTP score is obtained by adding the score for each of the 5 parameters.

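### The two-week history and physical exam is required after SBRT but discretionary after TACE, so toxicity and two CTP items are not ascertained alike in the two arms

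*Combined protocol and SAP*

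**What the plan says.** Section 7.0 gives each arm its own calendar for the treatment phase.

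- **SBRT (Table 2).** The column headed "2 Week Follow up post treatment (+/- 3 days" carries an unqualified X for history and physical exam. Weight, blood count, liver panel, sodium and renal tests, INR, toxicity, the liver scores and HRQL are also marked there.
- **TACE (Table 3).** Both two-week columns, after the initial TACE and after each later one, mark the exam as "X (per MD SOC only". The rows "Toxicity Notation" and "MELD-Na ALBI, and CTP assessment" have a plain X in the same columns, as do weight, labs and HRQL.

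Appendix A states: "CTP score is obtained by adding the score for each of the 5 parameters". The five are encephalopathy, ascites, bilirubin, albumin, and PT or INR. MELD-Na, by contrast, "relies on four readily available objective variables", all of them laboratory values.

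The synopsis lists the comparison of toxicity as a secondary objective, and section 15.0 describes the trial as non-blinded. Section 17.2.3 says: "Categorical outcomes like any retreatment, any toxicity, radiologic response, pathologic response will be described by counts, percent", with the arms compared by chi-square. The number of toxicities is compared by t-test.

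**The concern.** A toxicity comparison is fair only if both arms are examined for events in the same way. Here the rule for a clinical assessment follows the randomized assignment, so a larger sample would not remove the difference, and there is no blinding to limit it.

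Two things are at stake. The first is exam-dependent toxicity: a sign found by a clinician after SBRT may go unseen after TACE. History-taking sits in the same discretionary row, so the prompt for symptoms may differ too. The second is the early CTP score. Table 3 requires the score but leaves optional the assessment that would ordinarily supply two of its items. Section 2.3 suggests CTP may be useful for detecting worsening liver function and proposes to record it, so a two-week value obtained differently by arm is of limited use for that purpose.

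**Working it through.** **1. The plan's own toxicity figures.** Section 17.2.3 gives 99% and 95% as the chance of at least one event among 98 patients. The formula is 1 − (1 − p)^98.
- p = 0.05: 1 − 0.95^98 = 0.993.
- p = 0.03: 1 − 0.97^98 = 0.949.
- Widest 95% half-width: 1.96 × √(0.25/98) = 0.099.

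All agree with the plan. They assume that events which occur are recorded, and they say nothing about equal recording in the two arms.

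**2. The calendars side by side (Tables 2 to 4).**

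| Item | SBRT | TACE |
|---|---|---|
| Exam at two weeks | Required | Discretionary |
| Toxicity notation at two weeks | Required | Required |
| CTP at two weeks | Required | Required |
| Two-week labs | Required | Required |
| Exam on treatment days | None scheduled | Each TACE day |
| Post-baseline toxicity notations, treatment phase | 2 (last fraction, two weeks) | 2, 4 or 6 (for 1, 2 or 3 TACEs) |
| Required exams after last treatment day and before the 3-month visit | 1 | 0 |

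The 3-month visit is timed from randomization, so the gap after the last TACE varies with the number of treatments. It is clearest for a patient treated once.

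**3. Which measures depend on the exam.** The lab waiver in Table 3 ("If required labs were performed within 3 days of a TACE procedure, they do not have to be repeated") attaches to TACE-day labs only, so the two-week labs stand. It follows that:
- MELD-Na: 0 of 4 components need clinical assessment.
- ALBI (albumin and bilirubin): none.
- CTP: 2 of 5 items do, ascites and encephalopathy.

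**4. Illustration of size.** The documents give no capture rates, so every input here is assumed: true rate 40% in both arms; 95% of events recorded with an exam; 70 to 80% without one; half of TACE two-week visits without an exam; 98 per arm.
- SBRT recorded rate: 0.40 × 0.95 = 0.38.
- TACE at 70%: 0.40 × (0.5 × 0.95 + 0.5 × 0.70) = 0.33.
- TACE at 80%: 0.40 × (0.5 × 0.95 + 0.5 × 0.80) = 0.35.

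Exact rejection probability of the uncorrected two-sided 5% chi-square test:

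| Recorded SBRT v TACE | Rejects |
|---|---|
| 0.38 v 0.38 | 4.8% |
| 0.38 v 0.35 | 7.0% |
| 0.38 v 0.33 | 11.1% |

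This treats two weeks as the only chance to record an event. Suppose instead that half of the extra missed events are picked up at another visit, also an assumption. TACE rates become 0.38 − 0.03/2 = 0.365 and 0.38 − 0.05/2 = 0.355, and rejection falls to 5.4% and 6.3%. If three-quarters are picked up, it is 5.0 to 5.2%.

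**The case against.** The best defence is that the exam row is only one route to the data.

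- Toxicity notation is itself mandatory at two weeks in both arms. The grade 2 events that section 12.3.1 adds to the collection are abdominal pain, nausea, vomiting and fatigue, which can be elicited by asking. Section 14.0 has adverse events captured throughout. This stands, and it narrows the concern to exam-dependent findings and to how consistently patients are asked.
- A site must obtain ascites and encephalopathy status to comply with the CTP row. That is fair: the documents do not show that these items would be left blank or filled in by assumption. They also do not say how the items are obtained, and that gap remains.
- CTP change is not a listed secondary endpoint, section 17 names no CTP analysis, and the treatment-modification and removal rules in sections 8 and 10 do not use CTP. This stands. The scores are recorded for exploratory use.

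A reader might infer that TACE toxicity will be under-recorded overall and SBRT made to look worse. The documents do not support that. TACE has as many or more scheduled toxicity notations, an exam on each TACE day and an in-hospital recovery period (section 5.3), while no exam is scheduled during the SBRT fractions. Over the whole treatment phase the imbalance could run either way.

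A reader might also infer that liver decline in general is measured unequally. MELD-Na, ALBI and three CTP items rest on labs required in both arms.

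Finally, if no TACE patient were examined at two weeks, the recorded TACE rate in the illustration would be 28 to 32% and the test would reject in 14 to 32% of trials. Nothing in the documents suggests that standard of care amounts to no exams, so this should not be read as the expected effect.

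**Conclusion.** The concern holds in a limited form. By rule, the two-week clinical assessment differs by arm in an open-label trial that tests toxicity between arms. The findings at risk of being missed or scored differently after TACE are those that need an examination, together with the ascites and encephalopathy items of CTP. The risk is greatest after the last TACE, when no further exam is required until the 3-month visit.

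The direction of the net bias is not established. Its size cannot be derived from the documents: the illustrative rejection rates, from about 5% to 11% against 4.8%, depend entirely on the assumed capture rates, the assumed share of unexamined patients and the assumed recovery at other visits. The primary endpoint, sample size, alpha and the stated toxicity precision are untouched. The point merits correction because the asymmetry is avoidable and cheap to remove.

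**What to change.** Reconcile Tables 2 and 3 so that the two-week assessment is the same in both arms, with the exam requirement worded identically. Preferably, add one structured clinician form, used in both arms at that visit, that records ascites grade, encephalopathy grade and the four prespecified symptoms (abdominal pain, nausea, vomiting, fatigue). State that the two clinical CTP items are taken from this form, so that the score does not depend on whether a full exam was done.

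The cost is a change of calendar wording, one short form and a few minutes of clinician time per visit. The TACE two-week visit already requires weight, labs, toxicity, liver scores and FACT-Hep, so no new visit is needed. No figure in the statistical sections changes.

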**Table 4: Study Calendar for FOLLOW-UP (Both Arm A and Arm B)**

Follow-up After Initial Treatment Phase					
		3 months (+/- 4 weeks) post randomization	6 months (+/- 4 weeks) post Randomization	Q 3 months to 24 months post- randomization (+/- 4 weeks)	60 days post- transplantation (+/- 2 weeks)
History and Physical Exam		X	X	X	
Weight		X	X	X	
CBC with differential		X	X	X	
AST, ALT, Alk Phos, Bilirubin		X	X	X	
Na, BUN/Creatinine		X	X	X	
INR		X	X	X	
AFP (for HCC)		X	X	X	
Toxicity Notation		X	X	X	
Survival Status		X	X	X	X
MRI or CT of the abdomen  (mRECIST for HCC)		X	X	X	
Chest CT or X-ray 		X	X	X	
MELD-Na CP ALBI assessment		X	X	X	
Assessment of disease progression, recurrence and transplantation status		X	X	X	
HRQL 		X	X	X	
Mortality and Morbidity					X

 Scans will be obtained in accordance to liver transplantation protocols and timeframes and may not occur within the allotted time frame noted above. This will not be considered a protocol deviation as long as they are performed per United Network for Organ Sharing (UNOS) guidelines.

 HRQL questionnaire: FACT-Hep

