### 2.0 Secondary endpoints:

- Health related quality of life (HRQL) for both treatment arms
- Toxicity
- Number of further interventions
- Pathologic response of treated lesion(s)
- Radiologic response of treated lesion(s)
- 60 day Post-transplant morbidity and mortality

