### **12.2 Off Study Conditions**

- Subjects will be removed if they are unable to receive either SBRT or TACE due to decompensation prior to initial therapy.
- Subjects may be removed from the study at any time by subject request.
- Subjects who go on to receive additional non-radiation therapy (i.e., treatment that is not TACE or SBRT related) will be followed for progression within the treated lesion(s). They will no longer receive protocol-directed treatment or testing.
- Subjects who develop extra-hepatic tumor will not be followed and will be censored from the data analysis.
- Subjects who undergo a liver transplant will be considered off study and will not be followed from that time point (except to determine 60-day post transplantation survival status).
- Subjects permanently removed from Liver Transplant list and will not be followed.

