#### 12.4.4 SAE Reporting

All serious adverse events (SAE) (including death and hospitalization), premature withdrawal, and emergency treatment disclosures must be reported to the Project Manager at the Lahey Hospital & Medical Center within one working day. Applicable SAE forms should be completed in the electronic data capture system (EDC) within 10 days of their occurrence and updated as new information becomes available.

Medical and scientific judgment should be exercised in deciding whether expedited reporting is appropriate in other situations, such as important medical events that may not be immediately life-threatening or result in death or hospitalization, but may jeopardize the subject or may require intervention. All deaths occurring on study must be reported to the Lahey Hospital & Medical Center. These include deaths within 30 days of the end of study visits.

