## 16.0 Sample Size

This study is sized for hypotheses testing of improved time to residual or recurrent disease within the previously treated lesion(s) due to SBRT versus TACE treatment arms in the overall population of patients who are eligible for liver transplant and are on the waiting list. It is believed that more than 50% of patients will receive a transplant within 2 years of listing, but that far fewer patients will receive

a transplant within 1 year of study begin. Therefore we base power calculations on one year follow up and a drop rate of 15%. Based on initial data, we estimate a median time to residual or recurrent disease of 134 days in the TACE group. Based upon these numbers and a hazard ratio of 0.6 for the SBRT relative to the TACE group, a two-sided test controlling the overall type 1 error to 5% requires a total of 161 events (i.e. residual/recurrent disease) and about 131 patients per treatment arm to achieve a power of 90%. To achieve a power of 80%, a total of 120 events and about 98 patients per treatment arm are required. These calculations are made accounting for follow-up on patients once every three months where the calculated HR of 0.6 for this discrete model corresponds roughly to a HR of 0.54 if recurrent disease could be measured on the continuous time scale (days).

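### The 60-day post-transplant assessment may be completed from day 46, so morbidity up to day 60 is not ascertained in patients assessed early

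*Combined protocol and SAP*

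**What the plan says.** Section B, 2.0 lists "60 day Post-transplant morbidity and mortality" among the secondary endpoints; the Synopsis and Section 15.0 repeat it.

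Table 4 in Section 7.0 has one column after transplant: "60 days post- transplantation (+/- 2 weeks"). It is the only column marked for mortality and morbidity. It is also marked for survival status, and it asks for no examination, laboratory test or scan.

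Section 12.2 says: "Subjects who undergo a liver transplant will be considered off study and will not be followed from that time point". One exception follows in brackets: "except to determine 60-day post transplantation survival status". Morbidity is not named there.

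Section 17.2.3 gives the analysis: "Overall survival, and 60 day post-transplant morbidity and mortality will be described by Kaplan-Meier estimates, and groups compared using the log-rank test". A Cox model is added. No censoring rule is given for this endpoint; the rules in Sections 13.1 and 17.1 belong to the primary endpoint.

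Section 12.4.4 requires deaths on study to be reported and adds: "These include deaths within 30 days of the end of study visits". It does not say whether the post-transplant assessment is such a visit.

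**The concern.** A symmetric window suits a measurement taken at a visit. It does not suit a count of events over a fixed period, because that count is complete only once the period has ended. A site that closes the assessment on day 46 has followed the calendar but cannot report what happened on days 47 to 60. No further contact is required when the first one is early.

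At stake is whether this safety endpoint is fully observed in every transplanted patient, and whether patients seen early and late are counted over the same period. The primary endpoint, its event target and the sample size do not depend on it.

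**Working it through.** **Plan's own figure.** The documents give no sample size, power or event rate for this endpoint. The only figure to reproduce is the window: 60 - 14 = day 46 and 60 + 14 = day 74.

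**Gap for the earliest contact.** Days 47 to 60 are 14 days, and 14/60 = 23%.

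**Effect per patient if status is read without event dates.** Assume a 60-day risk P between 2% and 30% (not in the documents). Let H = -ln(1 - P) and F(t) = 1 - exp[-H(t/60)^k]. The hazard is constant when k = 1 and front-loaded when k = 0.5. The share of 60-day events missed at a day-46 reading is 1 - F(46)/P. The excess at a day-74 reading is F(74)/P - 1.

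| P | k | F(46) | missed at day 46 | F(74) | excess at day 74 |
|---|---|---|---|---|---|
| 2% | 1 | 0.0154 | 23.2% | 0.0246 | 23.0% |
| 2% | 0.5 | 0.0175 | 12.3% | 0.0222 | 10.9% |
| 5% | 1 | 0.0386 | 22.9% | 0.0613 | 22.6% |
| 5% | 0.5 | 0.0439 | 12.2% | 0.0554 | 10.7% |
| 10% | 1 | 0.0776 | 22.4% | 0.1219 | 21.9% |
| 10% | 0.5 | 0.0881 | 11.9% | 0.1104 | 10.4% |
| 30% | 1 | 0.2393 | 20.2% | 0.3559 | 18.6% |
| 30% | 0.5 | 0.2682 | 10.6% | 0.3271 | 9.0% |

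(Percentages come from unrounded values.) These are the extremes of the window; a contact nearer day 60 has a smaller error in either direction.

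**Averaged over the window.** Assume contacts are uniform from day 46 to day 74. Half fall before day 60, with a mean shortfall of 7 days. Over all patients that is 0.5 x 7 = 3.5 days, or 3.5/60 = 5.8% of the 60-day follow-up.

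**Events, as an illustration.** Section 16.0 expects more than half of patients to be transplanted within two years of listing. Take half of the 196 enrolled, 98 patients, of whom 49 are contacted early and 49 late. Average P - F(t) over days 46 to 60 for the events missed, and F(t) - P over days 60 to 74 for the events added:

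| P | k | missed | added | net |
|---|---|---|---|---|
| 5% | 1 | 49 x 0.00571 = 0.28 | 0.28 | about 0 |
| 5% | 0.5 | 49 x 0.00297 = 0.15 | 0.13 | -0.01 |
| 30% | 1 | 49 x 0.02995 = 1.47 | 1.39 | -0.08 |
| 30% | 0.5 | 49 x 0.01541 = 0.76 | 0.68 | -0.08 |

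The number 98 is an assumption. The statement in Section 16.0 counts from listing, and under Section 5.6 patients who meet the primary endpoint leave the study, so the number assessed after transplant could differ.

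**Deaths after an early contact.** If the post-transplant assessment is an end of study visit, the rule in Section 12.4.4 reaches day 46 + 30 = day 76 and covers the gap. If the study ends at transplant, as Section 12.2 suggests, it reaches about day 30 and does not. Neither reading covers non-fatal morbidity on days 47 to 60.

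**The case against.** A reader might infer that a death on day 55, after a day-46 contact, is never recorded. The documents do not support that. The exception in Section 12.2 names what must be determined, survival status at 60 days, and a day-46 contact alone does not determine it. Section 12.4.4 may also require the death to be reported. Both texts are ambiguous, so capture is possible but not assured. This part of the objection stands for deaths and does not help for morbidity.

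A reader might also infer that 60-day rates will be undercounted. That does not follow either. Section 17.2.3 plans Kaplan-Meier estimates, and a patient last seen on day 46 can be censored there. If early contact is unrelated to outcome and events are dated, the estimate is not systematically biased; it rests on fewer patients near day 60. In a percentage without dates, the late half of the window offsets the early half, and the two nearly cancel under uniform contact. A net undercount arises if late events are cut at day 60 while patients seen early are still counted as event-free, or if early contacts predominate. The plan says neither.

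Finally, sites might complete the column from records, and the same window applies to both arms, so nothing points to a difference between them. That is fair. But a record review closed on day 46 has the same gap, Table 4 does not ask for event dates, and no censoring rule is written for this endpoint. The protection that the Kaplan-Meier method offers is therefore available but not secured.

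**Conclusion.** The point holds in a limited form. Table 4 lets the only morbidity and mortality assessment be completed before the 60-day period ends. For patients assessed on days 46 to 59, morbidity up to day 60 is not ascertained, with a gap of up to 14 of 60 days (23%). For deaths, the gap depends on how Sections 12.2 and 12.4.4 are read.

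The consequence is lost information near day 60 under the planned analysis, and errors in both directions in an undated percentage. In the illustration, if every patient seen early were counted as event-free, about 0.15 to 0.28 events would be missed at a 5% risk and about 0.8 to 1.5 at a 30% risk. Those figures rest on assumed risks, hazard shapes, uniform contact times and 98 transplanted patients, none of which the documents state. This is a minor point on a secondary endpoint. It does not touch the primary endpoint, the sample size or the power.

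Separately, Section 12.2 keeps only survival status after transplant, while Section B, 2.0 and Table 4 include morbidity. These texts need to agree.

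**What to change.** 1. In Table 4, change the post-transplant window to 60 days (-0/+14 days), that is, day 60 to day 74.
2. Record the date of death and the onset date of each complication.
3. In Section 17.2.3, count events with onset on or before day 60, and censor at last contact any patient not followed to day 60. This also removes the overcount from late contacts.
4. In Section 12.2, extend the exception to 60-day morbidity, in line with Section B, 2.0 and Table 4. In Section 12.4.4, state whether the post-transplant assessment is an end of study visit.

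With these changes, the gap for an assessment made within the window falls from up to 14 days to none. The cost is one calendar entry, date fields on the form and a few sentences of text, with no extra visit. The downside is a scheduling window of two weeks where there are now four.
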